2.0 TRIAL DESIGN

2.1 Trial Design

This is a phase II single arm efficacy/safety trial that will evaluate the effectiveness of combining intensive locoregional intraperitoneal (IP) chemoimmunotherapy of cisplatin with IP rintatolimod (TLR-3 agonist) and IV infusion of the checkpoint inhibitor pembrolizumab (IVP) for patients with recurrent platinum-sensitive ovarian cancer (OC).

Patient cohort

This trial will enroll up to 45 patients; eligibility criteria include patients at first or second recurrence previously diagnosed with platinum-sensitive ovarian/fallopian tube carcinoma or primary peritoneal carcinomatosis. Platinum-sensitive OC is defined as patients with a treatment-free interval greater than 6 months. Patients must have at least one peritoneal lesion, measurable by CT/MRI scan. Patients will be allowed if RECIST 1.1 criteria is met for measurable retroperitoneal lesions if there also is the presence of peritoneal lesions during laparoscopy. The lesion should be large enough for biopsy and resection, ideally to yield greater than 2 grams of tumor for immunoassays. If biopsy is insufficient or not feasible during laparoscopy, patients may be allowed to proceed at the discretion of the PI if there are otherwise measurable lesions. All epithelial invasive histologies are included in this phase II design.

Patients will receive a total of six treatment cycles, at 3-week intervals (Schema 1, Section 2.2). We will use an IP neoadjuvant approach, followed by interval cytoreduction (usually laparoscopically) of residual tumor. The decision to perform interval cytoreductive surgery is at

the discretion of the treating physician. Cytoreduction will occur approximately 4 weeks after the fourth treatment cycle. Post-surgery we will consolidate with 2 additional courses of same chemo-immunotherapy regimen. Catheter will be removed 12 weeks after the last treatment. All surgical procedures, if done laparoscopically, are outpatient and will yield up to three serial biopsies of the tumor sites: 1) at catheter placement; 2) at interval cytoreduction which consists of removal of any visible tumor sites and the site biopsied initially whether tumor is present or not; 3) at catheter removal, when site of first tumor biopsy will be re-biopsied for pathologic response.

[figure not shown]
5

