We will characterize the immune response changes in each patient as measured by the total number of tumor-infiltrating CD3+CD8+ T cells (TILs) with the baseline evaluation of initial laparoscopic tumor biopsy when IP catheter is placed compared to interval surgical samples and laparoscopic biopsy at time of IP catheter removal. Changes in the frequency of T cells in the peritoneal washes at each cycle will also be evaluated. Since measurements of intra-patient changes in intra-tumoral CD8+ T cells before and after chemotherapy with chemokine modulation (in solid fraction of the tumor), as the primary endpoint of efficacy, were perceived as less reliable due to the difficulties in the longitudinal sampling of "representative" parts of tumor when comparing the original tumor biopsy to the resected tumors, and likely heterogeneous impact of chemotherapy on different parts of the tumors (resulting in the variations in immune infiltrates), such solid tumor evaluations will be performed as correlative studies and compared with the immune cell changes in the peritoneal fluid (which composition has also been shown to be predictive for the long-term outcomes in OC1. Frequent flushing of

the peritoneal catheter is standard of care at our institution to maintain catheter patency and assess for locoregional toxicity. It also allows collection of peritoneal samples.

7

Hypothesis:

We postulate that a treatment regimen that combines induction of locoregional immunogenic cell death using cisplatin and immune modulation through TLR-3 activation combined with immune checkpoint blockade via systemic anti-PD-1 which induces increased TILs and an improved anti-tumor T cell response. To test this hypothesis, we propose to:

- 1. Perform phase II clinical trial of combination IP cisplatin/rintatolimod chemoimmunotherapy plus IV pembrolizumab with efficacy clinical endpoints.
- 2. Identify the impact of combination treatment on the tumor immune microenvironment. This aim will evaluate the ability of the treatment to promote TIL accumulation, modulate biomarkers of immune exhaustion, and induce genes associated with cytotoxic anti-tumor immunity.

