3.3 Exploratory Objective

(1) **Objective:**

Correlative Studies

This represents the laboratory portion of our project and will test the hypothesis that IP administration of cisplatin and rintatolimod will result in expansion of type 1 immunity (CTL, NK-, and Th1 cells) in the peritoneal fluid and resected residual tumor mass of OC patients, an effect further increased by anti-PD1 immune checkpoint blockade.

Sample collection

Blood: Up to 30cc of blood will be collected serially in purple top (K2 EDTA) tubes, in conjunction with IP washes, at catheter placement and removal, during interval cytoreduction (decision to proceed with interval cytoreduction is at the discretion of the treating physician), and at each point where the intraperitoneal catheter is accessed for IP infusion (as further detailed below). Additionally, 10 cc of blood will be collected in a cell free DNA tube at IP port placement, interval surgery, and IP port removal.

Peritoneal cells and fluid: Peritoneal cells and fluid will be collected through the IP catheter during catheter flushes, necessary to maintain patency. Collection will occur at catheter placement and removal, and each time the catheter is accessed for IP infusion.

At each time point we will collect, whenever present, any spontaneously outflowing liquid (*IP fluid*). If there is 5 mL or greater return of IP Fluid, 2 mL will be sent for cell count and differential in a purple top (K2 EDTA) tube. If the sample does not yield a return then it is not sent for cell count and differential. We will also perform a "peritoneal wash", by injecting through the catheter 50 cc of sterile saline, followed by collection of the "peritoneal wash" fluid (*IP wash*, average of 8 cc expected). The dilution factor of the harvested cells (and soluble factors) in the IP wash or IP fluid will be evaluated by measuring the albumin concentration.

We will collect IP wash/fluid at days 1 (before treatment), 2 (before IV pembrolizumab, at end of IV pembrolizumab but before IP rintatolimod begins, and at the end of IP rintatolimod), and 3 of cycles 1-6. IP wash/fluid will also be collected at IP port placement, interval surgery and IP port removal.

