Note: Given the sensitivity of genomic assays and their requirement for little biological material (100ng RNA or DNA), all clinical specimens (blood, tumor, IP cells) will be processed first for RNA/DNA extraction. Remaining material will be used for live cell assays (like flow cytometry, for example), which typically require increased cell numbers.

RNA/DNA banked from these samples will be used in future ancillary genomic studies, to be separately conducted. For example, longitudinal profiling of the tumor mutanome would lead to a phylogenetic analysis of the evolution of tumor somatic mutations, and their potential for neoepitope formation. Analysis of $V\beta/J\beta$ usage landscape (ImmunoSeq) will assess changes in T cell receptor (TCR) clonality during treatment, and whether these changes correlate with clinical outcome. Such studies have the potential to identify changes in tumor heterogeneity during combination therapy. They will also teach us if and how "cold" OC tumors (low neoantigen load and low TILs) become "inflamed" (more mutated, higher TILs) during combination therapy.

3.3d. Perform mechanistic studies in vitro in human cells and cell lines and in vivo in mice to validate effector (or resistance) mechanisms triggered by combination therapy.

These experiments are designed to further dissect in vitro and in vivo the mechanisms responsible for the positive (or negative) effect of each of the three drugs used in our clinical trial and to assess their potential synergistic (or antagonistic) interactions.

For example, our preliminary data from mouse studies and early emerging data from patients in UPCI 11-128/NCT02615574 suggests that one of the pathways triggered by both cisplatin and rintatolimod involves DDX58/RIG-I and TRAIL. In addition, we identified that cisplatin-induced PDL1 up-regulation occurs in part via an activated Kras/Mek/Erk pathway. Results from this trial will further instruct us on the involvement of these pathways which we can subsequently dissect using pharmaceutical targeting with agonists and antagonists (for TRAIL, RIG-I etc.) or using OC cell lines with constitutive or conditional mutations in several oncogenic/tumor suppressor pathways, including Kras (Table A).

lleo b	Cell line nomenclature	Originating mouse genotype	Cell line genetic traits
derived lines	MOSE	MUC1+/-	Wild type Kras and Pten
OSE-6	M K OSE	MUC1 ^{+/-} LSL-Kras ^{G12D/+}	Silenced oncogenic KrasG12D

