We hypothesize that the dose of 200 mg of pembrolizumab, most widely used in current trials will also be well tolerated here.

We acknowledge that measurements of intra-patient changes in intra-tumoral CD8+ T cells (in the solid fraction of the tumor) before and after chemo-immunotherapy will be challenging, due to difficulties in longitudinal sampling of tumor when comparing the original biopsy to the resected tumors.

However, we note that our experience is in line with (or better than) a recent report from Tozzi et al ¹⁰, regarding increased feasibility, efficacy, and low morbidity of the laparoscopic resection during peritoneal debulking surgery. Two thirds of our patients in the UPCI 11-128/NCT02615574 study had completed interval debulking. In cases when laparoscopy is not possible, a minilaparotomy (1-day hospital stay) will be performed.

We are also aware of the likely heterogeneous impact of chemotherapy on different parts of the tumors (resulting in variations in immune infiltrates). To mitigate this, TIL evaluations will be performed as correlative studies and compared with the immune cell changes in the peritoneal fluid tumor-associated lymphocytes, which have also been shown to be predictive for the long-term outcomes in OC ¹¹.

In the eventuality that cellularity of peritoneal fluid is low, we will prioritize the sample processing for RNA extraction and RNAseq (instead of flow cytometry). This would allow us to measure the complete gene profiling of peritoneal resident cells and identify treatment-induced gene signatures. Based on our experience with 11-128, and given that 100 ng RNA would suffice for genomic platforms, we are confident that enough material will be obtained at each sample collection time point.

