8.0 STATISTICAL ANALYSIS PLAN

8.1 Statistical Analysis Plan Summary

Objectives

This trial will evaluate the anti-tumor efficacy of pembrolizumab in conjunction with IP cisplatin/rintatolimod. In addition to immunologic efficacy, a second objective is further monitoring of patient safety and adverse events. Provision is made to suspend the trial if unexpected and serious toxicities occur or if dose limiting toxicities (DLTs) from the list below in excess of 30% are observed:

- a) Any death not clearly due to the underlying disease or extraneous causes
- b) Any AE leading to a dose delay of greater than 14 days in initiation of cycle 2 will be considered a DLT
- c) A DLT is specifically defined as any of the following toxicities that occur related to any of the study interventions (cisplatin, rintatolimod, pembrolizumab) or the combination (as assessed by the Investigator) that occurs during the first cycle of treatment:
 - 1. Grade 3 renal toxicity
 - 2. Grade 2 or greater bronchospasm
 - 3. Grade 2 or greater allergic reaction or generalized urticaria
 - 4. Grade 2 or greater autoimmune reaction
 - 5. Grade 3 injection site reactions
 - 6. Grade 3 anaphylaxis
 - 7. Grade 2 pneumonitis
 - 8. ≥ Grade 3 hematologic toxicities lasting more than 48 hours, including neutropenia, thrombocytopenia and hemorrhage
 - 9. ≥ Grade 3 non-hematologic toxicities
 - 10. Grade 3 neurological symptoms
 - 11. Fever > 41°C, uncontrolled for over 4 hours in the absence of a medical cause
 - 12. Grade 3 diarrhea, Grade 3 skin toxicity, or Grade 3 liver function test increase
 - 13. Evaluation of liver toxicity as defined by Hy's Law:
 - The drug causes hepatocellular injury, generally shown by a higher incidence of 3-fold or greater elevations above the ULN of ALT or AST
 - Total Bilirubin>2xULN, without initial findings of cholestasis (elevated serum alkaline phosphatase)

Efficacy Study Design and Endpoints

The primary clinical endpoint is objective response. A secondary, translational endpoint is increase in the CD8 TIL infiltration in tumor and/or IP washes (pre-treatment vs post-treatment),

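### Tumor CD8 infiltration is measured as a total cell number across specimens whose sizes differ by design, and the SAP gives no unit or normalization

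*Combined protocol and SAP*

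**What the plan says.** **Tumor measure.** Section 3.1 (Biological Endpoints) characterizes immune change "as measured by the total number of tumor-infiltrating CD3+CD8+ T cells (TILs) with the baseline evaluation of initial laparoscopic tumor biopsy", "compared to interval surgical samples and laparoscopic biopsy at time of IP catheter removal". No denominator is given: not per gram, per unit area, or per live or CD45+ cell.

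**Specimens.** Section 2.1 describes three kinds. The first is a biopsy at catheter placement, "ideally to yield greater than 2 grams of tumor for immunoassays", and patients may proceed at the PI's discretion if that biopsy is insufficient or not feasible. The second is taken "at interval cytoreduction which consists of removal of any visible tumor sites and the site biopsied initially whether tumor is present or not". The third is a re-biopsy of the first site at catheter removal. No target or maximum size is set for the second or third.

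**Endpoint and analysis.** Section 8.1 defines the secondary translational endpoint as "increase in the CD8 TIL infiltration in tumor and/or IP washes (pre-treatment vs post-treatment"). Section 8.2 measures within-patient changes in CD8+ cells in tumor and peritoneal fluid at weeks 1, 8 and 12 and fits mixed linear models. It names no assay, unit or transformation, and no rule for samples without a result.

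**Washes.** Section 3.1 sets these on a frequency scale, for T cells. Section 3.3 adds: "The dilution factor of the harvested cells (and soluble factors) in the IP wash or IP fluid will be evaluated by measuring the albumin concentration". It also says that, if peritoneal cellularity is low, "we will prioritize the sample processing for RNA extraction and RNAseq (instead of flow cytometry").

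**Density.** Section 3.3a plans an IHC immunoscore that records the type, density and location of immune cells, including CD3+ and CD8+ cells; Section 3.3 (Sample preparation) assigns FFPE blocks to IHC. This is exploratory and is not linked to the endpoint in Section 8.

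**The concern.** Infiltration is a concentration: how many T cells there are for a given amount of tumor. A total number is that concentration multiplied by how much tissue the surgeon removed and the laboratory processed. Here the second factor changes between time points by design, from a biopsy to a resection of whatever is visible and back to a biopsy.

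Followed as written, the estimated change from baseline therefore combines a treatment effect on infiltration with a difference in specimen size. The mixed model in Section 8.2 cannot separate the two, since specimen mass or area is not in it. At stake is the trial's claim that the regimen promotes TIL accumulation, which is part of the hypothesis in Section 3.1.

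**Working it through.** The documents state no effect size, SD, power or sample size for the CD8 endpoint, so there is no plan figure to reproduce. The check is an identity plus illustrative values.

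**1. Tumor total.** Let T be the total count, D the density and M the tissue mass, so T = D × M. Then

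T_later / T_baseline = (D_later / D_baseline) × (M_later / M_baseline).

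The only specimen size in the documents is the ideal baseline yield above 2 g, so the mass ratios below are assumed.

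Density doubled:
- mass ratio 1.00: 2 × 1.00 = 2.0
- mass ratio 0.50: 2 × 0.50 = 1.0 (no apparent change)
- mass ratio 0.25: 2 × 0.25 = 0.5 (apparent halving)
- mass ratio 0.10: 2 × 0.10 = 0.2

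The total falls despite a true rise once the mass ratio is below 1 / (density ratio). For density rises of 1.5-, 2-, 3- and 5-fold this is 67%, 50%, 33% and 20%.

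Density unchanged, later specimen five times larger: 1 × 5 = 5, an apparent five-fold rise.

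On a density scale M cancels, and a doubling reads as 2.0 at every mass ratio.

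**2. Washes.** Section 3.3 instils 50 cc and expects about 8 cc back. With an assumed recovery of 4, 8 or 16 cc at constant concentration, a raw count varies by 4/8 = 0.5, 8/8 = 1 and 16/8 = 2. A frequency does not vary. Section 3.1 already names frequency, so the remaining gap is narrower: Section 8.2 does not repeat that scale, the frequency is of T cells rather than CD8+ cells, and it has no denominator. The denominator matters because Section 4.1.2 describes wash cells as a mixture that includes tumor cells and fibroblasts. A percentage of all cells can rise because tumor cells disappear; a percentage of leukocytes does not have that problem.

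**3. Washes without flow.** Log CD8 counts were simulated for 1,000,000 pairs per scenario. Assumptions: SD 0.5 or 1.0, within-patient correlation 0.3 or 0.6, and values below the baseline 10th or 30th percentile unobserved at both times.
- True rise 0.5 log units, 10% of baseline values lost: complete pairs give 0.42 to 0.47; all available values give 0.39 to 0.42.
- True rise 0.5, 30% lost: complete pairs give 0.33 to 0.42; all available values give 0.28 to 0.32.
- No true change: bias about 0.

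This is a rough guide. It removes values by CD8 count, whereas the protocol's switch acts on total cellularity, and it uses simple contrasts rather than the planned mixed model.

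**4. Timing.** The flow chart (Section 6.1) has washes pre-treatment, at weeks 2, 5, 8, 11, 15-16, 19 and 22, at safety follow-up and at week 31. Tumor is obtained pre-treatment, at weeks 15-16 and at week 31. Of weeks 1, 8 and 12 in Section 8.2, only week 8 has a column, and no tumor is taken then.

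**The case against.** The best defense is that the protocol knows tumor sampling is weak. Sections 3.1 and 3.3 call longitudinal tumor CD8 measurement less reliable, make it correlative and compare it with peritoneal fluid. Density is already to be recorded by IHC, and Section 8.1 speaks of infiltration, so total number may be loose wording. This lowers the stakes but does not remove the point. The reasons given for unreliability are representativeness and heterogeneity, not specimen size, and nothing in Section 8 directs the analyst to density instead of the total.

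A reader might go further in five ways that the documents do not support.

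- *That wash counts are also confounded by dilution.* The total-number wording covers tumor only. Washes are on a frequency scale, and albumin is measured.
- *That tumor shrinkage makes the total fall by a calculable amount in responders.* That would need the whole lesion counted both times. Baseline is a biopsy, and the interval resection may be larger or smaller.
- *That low-count visits drop out and post-treatment CD8 is overstated.* The switch depends on total cellularity, not the CD8 value, and applies at baseline too. In the simulated scenarios a rise was understated and none was created. If cellularity fell mainly after treatment, the direction could differ.
- *That a rise in either compartment counts as success.* The and/or wording is loose, but no success rule is attached to it; Section 8.2 only estimates changes.
- *That flow should precede RNA extraction.* "Remaining material will be used for live cell assays" is a laboratory trade-off for which Section 3.3 gives its reason: genomic assays need little material.

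**Conclusion.** The concern holds for the tumor scale. A total number compared across a biopsy, a resection and a re-biopsy does not measure infiltration, and the SAP does not correct it. The error has no fixed sign. Its size equals the mass ratio, which the documents do not allow anyone to estimate; the break-even of 50% for a doubled density and the five-fold false rise are illustrations. The identity assumes only that the count comes from the tissue actually taken.

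The wash part reduces to an unspecified denominator and a scale not carried into Section 8.2. The low-cellularity part reduces to a missing threshold and a missing sensitivity analysis, with the direction of bias left open. All of this concerns a secondary translational endpoint with no stated power or decision rule. The primary response-rate decision and the safety monitoring are unaffected. The change is worth making because a better scale is already planned.

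**What to change.** - **Tumor.** In Sections 3.1, 8.1 and 8.2, replace the total number with CD3+CD8+ density (cells per mm2) by IHC on FFPE sections. Section 3.3a lists CD3+ and CD8+ cells without saying whether they are co-stained; if they are not, state that CD8+ density is used. Say what is recorded when the re-sampled site contains no tumor.
- **Wash.** In Section 8.2, use CD8+ cells as a percentage of leukocytes by flow cytometry, with an albumin-corrected count as support.
- **Reporting.** Replace the and/or wording in Section 8.1 with separate tumor and wash results.
- **Missing flow data.** State the cellularity threshold for the switch to RNAseq. Report how many washes lack flow data at each visit, and add a sensitivity analysis for them without presuming the direction of bias.
- **Timing.** Reconcile weeks 1, 8 and 12 in Section 8.2 with the collection times in Section 6.1.

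The cost is wording and a little more analysis work, as IHC and albumin are already planned. The tumor result will depend on adequate FFPE tissue at each time point. Density does not cure the sampling heterogeneity that the protocol acknowledges; it removes only the dependence on specimen size.

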3.2 Secondary Objective(s) & Hypothesis(es)

(1) Objective:

Toxicity Endpoints

In addition to clinical and immunologic efficacy, a secondary objective is further monitoring of patient safety and adverse events. Provision is made to suspend the trial if unexpected and serious toxicities occur as outlined in study procedures section. Anticipated toxicities such as renal toxicity or locoregional toxicities of IP therapy will be monitored weekly. Patients will also be closely monitored for immune related toxicities (pneumonitis, colitis, hepatitis, endocrinopathies, nephritis, and infusion related toxicities). Dose adjustments and schedule adjustments will be made according to guidelines for key toxicity parameters, outlined below in study procedures section.

3.3 Exploratory Objective

(1) **Objective:**

Correlative Studies

This represents the laboratory portion of our project and will test the hypothesis that IP administration of cisplatin and rintatolimod will result in expansion of type 1 immunity (CTL, NK-, and Th1 cells) in the peritoneal fluid and resected residual tumor mass of OC patients, an effect further increased by anti-PD1 immune checkpoint blockade.

Sample collection

Blood: Up to 30cc of blood will be collected serially in purple top (K2 EDTA) tubes, in conjunction with IP washes, at catheter placement and removal, during interval cytoreduction (decision to proceed with interval cytoreduction is at the discretion of the treating physician), and at each point where the intraperitoneal catheter is accessed for IP infusion (as further detailed below). Additionally, 10 cc of blood will be collected in a cell free DNA tube at IP port placement, interval surgery, and IP port removal.

Peritoneal cells and fluid: Peritoneal cells and fluid will be collected through the IP catheter during catheter flushes, necessary to maintain patency. Collection will occur at catheter placement and removal, and each time the catheter is accessed for IP infusion.

At each time point we will collect, whenever present, any spontaneously outflowing liquid (*IP fluid*). If there is 5 mL or greater return of IP Fluid, 2 mL will be sent for cell count and differential in a purple top (K2 EDTA) tube. If the sample does not yield a return then it is not sent for cell count and differential. We will also perform a "peritoneal wash", by injecting through the catheter 50 cc of sterile saline, followed by collection of the "peritoneal wash" fluid (*IP wash*, average of 8 cc expected). The dilution factor of the harvested cells (and soluble factors) in the IP wash or IP fluid will be evaluated by measuring the albumin concentration.

We will collect IP wash/fluid at days 1 (before treatment), 2 (before IV pembrolizumab, at end of IV pembrolizumab but before IP rintatolimod begins, and at the end of IP rintatolimod), and 3 of cycles 1-6. IP wash/fluid will also be collected at IP port placement, interval surgery and IP port removal.

Tumor tissue: Tumor biopsy (typically obtained laparoscopically) will be collected at baseline (at catheter insertion), after four treatment cycles, during cytoreductive surgery, and at time of IP port removal if feasible. The primary tumor biopsy site will be marked by a surgical clip so it can be assessed by biopsy at subsequent laparoscopic surgery.

Sample preparation

Tumors will be immediately processed for FACS and genomic profiling, or they will be dissociated and frozen viably in 10% DMSO-containing cryopreservation medium. For FACS and genomic profiling, the tumor will be minced into 1mm pieces and single cells dissociated with liberase. A portion of the tumor tissue will also be placed in formalin, followed by paraffin embedding. FFPE blocks will be used for immunohistochemistry (IHC).

IP cells and supernatants will be separately cryopreserved, until ready to use.

Using these clinical specimens, we propose to:

3.3a. Identify longitudinal phenotypic changes of immune cell subsets in the blood and tumor microenvironment (tumor tissue, IP fluid, and IP wash).

These experiments will test the hypothesis that treatment increases the accumulation of activated effector cytotoxic, granzyme B^{high} CD8 T and of CD4 Tbet^{high} Th1 cells, while also monitoring the accumulation of immune suppressive cells CD4+FOXP3+ Tregs and/or

MDSCs (CD11b+CD33+DRlow/-). T cell exhaustion markers (PD1, PDL1, LAG3, TIM3, EOMES etc.) ^{1,2} will also be monitored in the blood, tumor, and peritoneal fluid/washes via multicolor flow cytometry. Flow cytometry assays will be performed by [name] lab (Co-PI) at the Magee-Womens Research Institute (MWRI) Flow Core. [name] serves as the MWRI Flow Core Director.

In parallel with T cell immunity, we will monitor changes in humoral anti-tumor immunity, focusing primarily on antibodies to MUC1 and MUC16 (CA125) tumor antigens. We postulate that increase in new IgG1 tumor antigen specific responses are indicative of Th1 immunity and positively correlate with cytotoxic anti-tumor responses ³. Antibody responses will be tested using commercial ELISA kits, as per our previously published results ⁴.

Tumor immunoscore will measure in situ immune infiltrates ⁵, by recording the type, density, and location of immune cells within the tumor samples. Using IHC we will focus on CD3+ T cells, CD8+ cytotoxic T cells (CTL), and CD45RO+ memory T cells, which are typically associated with a longer disease-free survival.

Tissue PDL1 expression will be determined by IHC using the anti-PDL1 clone 22C3 IHC detection assay and will instruct us on the frequency of PDL1 positive cells and their tumor vs stroma distribution.

All these T cell and tumor cell biomarkers will be further validated through orthogonal approaches (NanoString, RNAseq), as routinely employed by us (Fig. 1, 4, and 5) and as further described below.

3.3b. Measure systemic and locoregional changes in immune modulatory chemokines and cytokines.

We will focus on the relative expression of effector to suppressor cytokines and chemokines, in serum/plasma and IP wash/fluid. We postulate that treatment will induce increased effector cytokines (consistent with Th1/CTL responses) and reduce secretion of suppressive chemokines. Among the effector cytokines/chemokines we will measure IFNγ and IFNγ and IFNγ-induced cytokines, like CXCL9, CXCL10, CXCL12, IL-12p70, IL-18, and IL-23. Among the suppressor cytokines, we will focus on IL-10 and TGBF-β. Selection of these candidates is guided by our preliminary data, especially from studies on rintatolimod, either alone or in combination with cisplatin (NCT02432378) and from in vivo studies in mice treated with anti-PDL1 ⁶. All measurements will use ELISA arrays as previously employed by us ^{4,7,8}.

3.3c. Perform transcriptomic analyses to identify treatment-induced changes in tumor inflammation.

The effect of therapy can be best appreciated when blood and all key components of the tumor are simultaneously examined in a longitudinal approach. In addition to the focused analyses described above (in 3.3a and 3.3b), using defined phenotypic and functional markers of immune cell subsets in blood, tumor, and IP fluid/wash, we will also perform RNAseq which will provide information of the whole tumor transcriptome, including genes used for the above

phenotypic profiles. Additional markers identified at the RNA level will be further confirmed at the protein level, via flow cytometry, IHC, Western Blot or ELISA, depending on availability of detection antibodies.

All genomic profiling assays will be guided by expertise from [name] co-investigator on this project. Bioinformatic analyses will be performed with guidance from [name], Co-investigator on this project.

Note: Given the sensitivity of genomic assays and their requirement for little biological material (100ng RNA or DNA), all clinical specimens (blood, tumor, IP cells) will be processed first for RNA/DNA extraction. Remaining material will be used for live cell assays (like flow cytometry, for example), which typically require increased cell numbers.

RNA/DNA banked from these samples will be used in future ancillary genomic studies, to be separately conducted. For example, longitudinal profiling of the tumor mutanome would lead to a phylogenetic analysis of the evolution of tumor somatic mutations, and their potential for neoepitope formation. Analysis of $V\beta/J\beta$ usage landscape (ImmunoSeq) will assess changes in T cell receptor (TCR) clonality during treatment, and whether these changes correlate with clinical outcome. Such studies have the potential to identify changes in tumor heterogeneity during combination therapy. They will also teach us if and how "cold" OC tumors (low neoantigen load and low TILs) become "inflamed" (more mutated, higher TILs) during combination therapy.

3.3d. Perform mechanistic studies in vitro in human cells and cell lines and in vivo in mice to validate effector (or resistance) mechanisms triggered by combination therapy.

These experiments are designed to further dissect in vitro and in vivo the mechanisms responsible for the positive (or negative) effect of each of the three drugs used in our clinical trial and to assess their potential synergistic (or antagonistic) interactions.

For example, our preliminary data from mouse studies and early emerging data from patients in UPCI 11-128/NCT02615574 suggests that one of the pathways triggered by both cisplatin and rintatolimod involves DDX58/RIG-I and TRAIL. In addition, we identified that cisplatin-induced PDL1 up-regulation occurs in part via an activated Kras/Mek/Erk pathway. Results from this trial will further instruct us on the involvement of these pathways which we can subsequently dissect using pharmaceutical targeting with agonists and antagonists (for TRAIL, RIG-I etc.) or using OC cell lines with constitutive or conditional mutations in several oncogenic/tumor suppressor pathways, including Kras (Table A).

lleo b	Cell line nomenclature	Originating mouse genotype	Cell line genetic traits
derived lines	MOSE	MUC1+/-	Wild type Kras and Pten
OSE-6	M K OSE	MUC1 ^{+/-} LSL-Kras ^{G12D/+}	Silenced oncogenic KrasG12D

	M K OSE-AdCre	MUC1+/-LSL-Kras ^{G12D/+}	Active oncogenic KrasG12D
	MOSE-p53	MUC1+/-	CRISPR/Cas9 edited p53 loss
	MPOSE	MUC1 ^{+/-} Pten ^{loxP/loxP}	Silenced Pten deletion
	M P OSE-AdCre	MUC1 ^{+/-} Pten ^{loxP/loxP}	Pten deletion
	M KP -T	MUC1 ^{+/-} LSL-Kras ^{G12D/+}	Kras LOH and
		Pten ^{loxP/loxP}	Pten deletion
	2F8 and 2F8cis	MUC1 ^{+/-} LSL-Kras ^{G12D/+}	Kras LOH and
lines		Pten ^{loxP/loxP}	Pten deletion
lla cell	M KP -Liver	MUC1 ^{+/-} LSL-Kras ^{G12D/+}	Oncogenic KrasG12D and
Tumor-derived cell lines		Pten ^{loxP/loxP}	Pten deletion
io mn	M KP -Lung	MUC1 ^{+/-} LSL-Kras ^{G12D/+}	Oncogenic KrasG12D and
		Pten ^{loxP/loxP}	Pten deletion

Table A. Genetic traits of our novel murine OC cell lines, to be used in this project. Bold letters denote genetic modifications in either Kras (K), Pten (P) or both (KP). Letter M denotes presence of MUC1 transgene. Top rows: OSEderived cell immortalized transformed as per Roby et al 9. MOSE-p53 cells are defective in p53, post CRISPR/Cas9 editing of MOSE cells. Bottom rows: tumor-derived cell lines, which have been passaged until stable proliferation rate was obtained. Clone 2F8 was obtained via limiting dilution of MKP-T cells 8. Clone 2F8cis are cisplatin-resistant derivatives of 2F8 cells. Until recently, preclinical modeling of OC largely relied on two murine cell lines- ID8 and IG10derived from ovarian

surface epithelium (OSE) ⁹. We (the [name] Lab) recently developed the largest collection of new murine cell lines with well-defined genetic traits (Table A and reference ⁸.

In addition to cell lines derived from mice with endometrioid (Kras and Pten driven tumors- ⁸, we have recently generated a CRSPR/Cas9 engineered, p53-deleted OC cell line that triggers aggressive IP tumors with high grade serous histology.

Anticipated results, potential pitfalls, and alternative approaches:

Completion of this project will allow us to identify signals of efficacy based on changes in tumor dimensions between first and second surgery as measured at laparoscopy. It will test whether treatment promotes CTL infiltration into the tumor microenvironment, and measure the magnitude and duration of this effect.

We expect to see responses in platinum-sensitive disease so the nature of infiltrate in the residual tumor site will provide histologic evidence of inflammatory cell death. We will also assess the safety profile of the novel IP cisplatin/rintatolimod and IV pembrolizumab treatment combination.

We hypothesize that the dose of 200 mg of pembrolizumab, most widely used in current trials will also be well tolerated here.

We acknowledge that measurements of intra-patient changes in intra-tumoral CD8+ T cells (in the solid fraction of the tumor) before and after chemo-immunotherapy will be challenging, due to difficulties in longitudinal sampling of tumor when comparing the original biopsy to the resected tumors.

However, we note that our experience is in line with (or better than) a recent report from Tozzi et al ¹⁰, regarding increased feasibility, efficacy, and low morbidity of the laparoscopic resection during peritoneal debulking surgery. Two thirds of our patients in the UPCI 11-128/NCT02615574 study had completed interval debulking. In cases when laparoscopy is not possible, a minilaparotomy (1-day hospital stay) will be performed.

We are also aware of the likely heterogeneous impact of chemotherapy on different parts of the tumors (resulting in variations in immune infiltrates). To mitigate this, TIL evaluations will be performed as correlative studies and compared with the immune cell changes in the peritoneal fluid tumor-associated lymphocytes, which have also been shown to be predictive for the long-term outcomes in OC ¹¹.

In the eventuality that cellularity of peritoneal fluid is low, we will prioritize the sample processing for RNA extraction and RNAseq (instead of flow cytometry). This would allow us to measure the complete gene profiling of peritoneal resident cells and identify treatment-induced gene signatures. Based on our experience with 11-128, and given that 100 ng RNA would suffice for genomic platforms, we are confident that enough material will be obtained at each sample collection time point.

